### **12.2.1 Adverse Events**

All AEs occurring during the study will be recorded and classified on the basis of MedDRA terminology. Descriptions of AEs will include the date of onset, the date the AE ended, the severity of the AE, the relationship to study drug, the action taken regarding study drug usage, the action taken to treat the AE, and the outcome. All reported treatment-emergent AEs (TEAEs) will be summarized by the number of Subjects reporting AEs, system organ class, preferred term, severity, seriousness, and relationship to study drug. TEAEs are those AEs with an onset on or after the date of the first study drug application.

Adverse events will be summarized by treatment group and severity. Each subject will be counted only once within a system organ class or a preferred term by using the adverse events with the highest severity within each category.

Adverse events will be summarized by treatment group and relationship to study drug. Each subject will be counted only once within a system organ class or a preferred term by using the adverse events with the greatest relationship within each category.

Comparisons among treatment groups will be made by tabulating the frequency of subjects with one or more AEs (classified into MedDRA terms) during the study. The Fisher's Exact test will be used to compare the percentage of subjects in each treatment group who report any adverse event at a significance level of 0.05. The specific system organ classes and preferred terms analyzed will be those that are reported by at least one percent of the subjects in any treatment group.

All information pertaining to AEs noted during the study will be listed by subject, detailing verbatim given by the investigator, preferred term, system organ class, start date, stop date, severity, actions taken, and drug relatedness. The AE onset will also be shown relative (in number of days) to the day of initial dose of the randomized study drug.

Serious adverse events (SAEs) will be tabulated by subject within treatment groups.

In addition, a list of subjects who discontinued from the study and a list of subjects who experienced SAEs will also be provided.

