### **11.1 Schedule of Evaluations and Procedures**

#### **11.1.1 Visit 1: Screening Visit (Day -35 to 0)**

The following procedures will be conducted at this visit:

1. Obtain written informed consent prior to performing any study procedures. Subjects less than the age of consent must sign an assent form, and the parent or legal guardian must sign the informed consent form.
2. Assign the subject a 6-digit subject number by accessing IWRS, which will consist of the 3-digit site number (pre-assigned to each site) and the 3-digit chronological order screening number, assigned by the IWRS and starting with 101 (eg, 101001, 101002, etc.; in this example site number is 101).
3. Record the subject's demographic information.
4. Record the subject's medical history.
5. Record all previous medications (including acne medications) for the past 4 weeks (past 6 months for systemic retinoids). Record any therapies that will be used concomitantly during the study.
6. Perform Evaluator's Global Severity Score (EGSS) assessment followed by inflammatory lesion count and non-inflammatory lesion count.
7. Perform a Urine Pregnancy Test for all females who are pre-menses and females of childbearing potential. The urine pregnancy tests will be supplied by the CRO or CRO

vendor. Verify that the subject meets the applicable inclusion/exclusion criteria as outlined in Sections 8.1 and 8.2.

8. Discuss allowed cleansers, moisturizers and sunscreens and record any cleanser, moisturizer and sunscreen use. (Appendix 17.2).
9. If subject wears makeup, remind the subject not to wear make-up during any future visits.
10. If the subject requires a washout, schedule the Baseline visit to occur after the washout is complete. If no washout is required, the Screening and Baseline visits may occur on the same day.

*A urine pregnancy test must be completed at the Screening and Baseline visits prior to randomization, and at all scheduled study visits. The decision may be made by the investigator to do additional pregnancy tests during the course of the study.*

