### **11.1.3 Visit 3: Week 2 (Day 14 ± 3 Days) Visit**

The following procedures will be conducted at this visit (if a subject terminates early, all final visit (Week 12/Final Visit) procedures must be performed, if possible):

1. The Evaluator will perform the efficacy evaluations including the Evaluator's Global Severity Score (EGSS), inflammatory lesion counts, and non-inflammatory lesion counts. The EGSS is performed prior to the lesion counting. Every effort should be made for the same qualified and validated evaluator to perform the efficacy evaluations at all visits from Baseline to Week 12 visit for the same subject.
2. The Evaluator will perform Cutaneous Safety and Tolerability Evaluations.
3. Record changes in any concomitant medications or therapies since the previous visit under Prior and Concomitant Medications or Therapies. Check for prior and concomitant medications / therapies as per Section 9.4.

4. Record any new AEs reported spontaneously by the subject or changes in any ongoing AEs.
5. Perform a Urine Pregnancy Test for all females who are pre-menses and females of childbearing potential.
6. The study drug technician will retrieve and weigh the used study drug with the cap on to the nearest 0.1 gram. Note: a new pump will NOT be dispensed at this visit. The original pump will be re-dispensed back to the subject.
7. The study diary calendar will be collected and reviewed for compliance. Any missed doses or deviations should be reported. A new study diary calendar will be dispensed.
8. *Select Sites Only* – Obtain representative photographs of the face.
9. The study coordinator or designee will remind the subject of the proper technique for application of study drug (section 10.1.3). At this visit, the subject will apply the study drug at the investigational center under the direction of the study coordinator or designee to confirm proper technique. Any necessary retraining can be completed. The study drug should be applied **after** all clinical assessments. The study coordinator or designee will remind the subjects to apply the study drug once daily at home in the evening up to evening prior to Week 12 visit (study drug will not be applied in the evening after this study visit).

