## **11.4 Adverse Events**

### **11.4.1 Definition of Adverse Event**

An AE is any untoward medical occurrence in a patient or clinical investigation subject administered a medicinal product and which does not necessarily have a causal relationship with the study drug. AEs include any unfavorable and unintended illness, sign, symptom, clinically significant laboratory test abnormality, or disease temporally associated with the use of a

medicinal product that has appeared or worsened during the course of the clinical trial, regardless of causal relationship to the study drug(s) under study. AEs include any illness, sign, symptom, or out-of-range and clinically significant laboratory finding that has appeared or worsened during the course of the clinical trial, regardless of causal relationship to the study. The collection of non-serious AEs and serious adverse events (SAEs) will begin following the subject's completion of the consent process to participate in the study.

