#### **11.4.2 Documenting Adverse Experiences**

It is the responsibility of the investigator to document all AEs that occur during the course of the study. The AEs should be documented as a single medical diagnosis. When this is not possible, the AE should be documented in terms of signs and/or symptoms observed by the investigator or reported by the subject at each study visit. Each AE which appears to be independent of any prior event will be reported separately.

All AEs occurring after the subject signs the informed consent through the last study visit must be reported, regardless of whether or not the AEs are considered drug-related. All AEs, whether in response to a query, observed by the study site personnel, or reported spontaneously by the subject, will be recorded. Any AEs deemed related to treatment reported or observed at the final study/treatment visit will be followed until stabilization or resolution (or up to 30 days after final study visit).

At each visit during the study, the subject will be assessed for the occurrence of new and ongoing AEs. Cutaneous tolerability signs and symptoms that result in the subject's requiring a concomitant therapy, interruption of treatment, or discontinuation from the study will be reported as an AE. The following data will be collected on all AEs and recorded on the appropriate eCRF:

- Event name (diagnosis preferred, if unknown, record the signs/symptoms)
- Onset date and end date
- Maximum intensity (severity)
- Seriousness
- Action taken regarding study drug
- Corrective treatment, if given
- Outcome

In addition, the investigator's assessment of causality will be recorded.

Vital sign abnormalities are to be recorded as AEs only if they are clinically significant (for example: are symptomatic, requiring corrective treatment, leading to discontinuation or fulfilling a seriousness criterion).

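### TEAEs are defined by onset date alone, so a screening-onset event that worsens on study drug is left out of the TEAE summaries, and the scope of the group comparison is ambiguous

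*Combined protocol and SAP*

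**What the plan says.** All references are to the combined protocol and SAP.

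- **TEAE definition (12.2.1):** "TEAEs are those AEs with an onset on or after the date of the first study drug application". There is no clause for worsening. Summaries of TEAEs are planned by number of subjects, system organ class, preferred term, severity, seriousness and relationship.
- **AE definition (11.4.1):** an AE includes an illness, sign or symptom temporally associated with a "medicinal product that has appeared or worsened during the course of the clinical trial, regardless of causal relationship to the study drug(s) under study".
- **Collection period (11.4.2):** "All AEs occurring after the subject signs the informed consent through the last study visit must be reported". Under 11.1.1, screening may run from Day -35 to Day 0.
- **Record-keeping (11.4.2, 11.4.4):** "Each AE which appears to be independent of any prior event will be reported separately". Each event carries an onset date and a maximum severity.
- **Visit steps (11.1.3, repeated at Weeks 4, 8 and 12):** "Record any new AEs reported spontaneously by the subject or changes in any ongoing AEs". The Baseline steps (11.1.2) likewise carry forward changes in events seen since screening.
- **Group comparison (12.2.1):** Fisher's exact test is used to "compare the percentage of subjects in each treatment group who report any adverse event at a significance level of 0.05". The severity and relationship paragraphs also refer to adverse events, not TEAEs. The Synopsis safety text has the same wording and does not mention TEAEs.

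**The concern.** The AE definition has two limbs, appearance and worsening. The TEAE definition keeps only the first. Because collection begins before dosing, some events can be open at Day 0, and for those the on-drug worsening is the part that bears on the drug. A rule based on onset alone classes such an event by its start and ignores what happened on treatment.

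The same section is also unclear about which events enter the severity, relationship and Fisher analyses. Two programmers could produce different tables and p-values from it. Safety and tolerability are part of the primary objective (Section 6), so both points should be settled before unblinding. Efficacy conclusions are not touched.

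**Working it through.** The plan states no figure on this point, so the main check is to follow one event through the text.

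**Step 1: an event that starts in screening and worsens on drug.** Take any AE with onset at Day -10 that does not bar enrolment, is ongoing at Day 0 and becomes more severe at Day 20.

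1. It is reportable from onset, because collection starts at consent (11.4.1, 11.4.2).
2. At Day 20 the visit step treats it as a change to an ongoing event. It is not independent of a prior event, so 11.4.2 does not call for a separate record.
3. The record keeps its Day -10 onset and takes the worse grade as its maximum severity (11.4.2, 11.4.4).
4. Day -10 is before the date of first application, so 12.2.1 does not class it as a TEAE.

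By contrast, a condition present before consent that worsens on drug becomes an AE under 11.4.1 at the time of worsening. If dated from then, it is a TEAE. The two cases differ only in whether the condition began before or after consent.

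**Step 2: where the event still appears.**

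| Output | Limited to TEAEs? | Worsened screening event |
|---|---|---|
| TEAE summaries (12.2.1) | Yes | Missing |
| Severity, relationship and Fisher analyses, read literally | No | Counted, but so are purely pre-dose events |
| The same analyses, read as TEAEs | Yes | Missing |
| By-subject AE listing (12.2.1) | No | Present, with onset relative to first dose |
| SAE tabulation, list of discontinued subjects (12.2.1), disposition (12.3) | No | Present where applicable |
| Cutaneous safety and tolerability scores by visit (12.2) | Not AE-based | Local signs visible from Baseline to Week 12 |

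**Step 3: length of the pre-dose window.** At most 35 days, against 84 days of treatment: 35/(35 + 84) = 29% of the collection period. This is a maximum. When no washout is needed, screening and Baseline may be on the same day and the window is close to zero.

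**Step 4: how many subjects (assumed rates; the documents give none).** Suppose 2% to 10% of 300 per arm have an AE ongoing at Day 0, and 10% to 25% of those worsen on drug.

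- Low: 300 × 0.02 × 0.10 = 0.6 subjects per arm
- High: 300 × 0.10 × 0.25 = 7.5 subjects per arm

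These are totals over all terms.

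**Step 5: dilution if pre-dose events are admitted (assumed rates).** Let a fraction q of each arm have a pre-dose AE, equal in both arms and independent of on-treatment events. The any-AE rate becomes 1 − (1 − p)(1 − q), so the difference between arms becomes (1 − q)(p₁ − p₀). With p₁ = 20%, p₀ = 12%, 300 per arm and a two-sided Fisher test at 0.05, with power by exact enumeration:

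| q | Rates | Difference (points) | Power |
|---|---|---|---|
| 0 | 20.0% vs 12.0% | 8.0 | 73.3% |
| 3% | 22.4% vs 14.6% | 7.8 | 65.3% |
| 5% | 24.0% vs 16.4% | 7.6 | 60.5% |
| 10% | 28.0% vs 20.8% | 7.2 | 50.1% |

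Power falls faster than the difference because the added events also raise the variance.

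**The case against.** The strongest reply is that the two defects largely exclude each other. If the severity, relationship and Fisher paragraphs cover all AEs, worsened screening events are counted there at their highest severity and greatest relationship. If those paragraphs mean TEAEs, which is natural because they follow the TEAE sentence, the pre-dose problem disappears. This stands: the two defects cannot both apply in full to the same tables. But each reading has one of them, and the text does not say which reading is meant.

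A second reply is that local irritation, the most obvious candidate, is mostly captured elsewhere. Scaling, erythema, pigmentation, itching, burning and stinging are scored at Baseline and every later visit and summarised by arm. They must be reported as AEs only when they lead to concomitant therapy, interruption or discontinuation (11.3.1, 11.4.2). This also stands, and it lowers the stakes.

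Third, a site could open a new record when an event worsens. Nothing forbids it and 11.4.1 gives some support, but nothing requires it and the visit steps point the other way. The separate SAP promised in Section 12 might settle both points; it is not in the text reviewed.

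A reader might also infer more than the documents support:

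- *That the event disappears from all safety reporting.* It does not; see Step 2.
- *That facial dermatitis ongoing from screening is the typical case.* Exclusion 2 names dermatitis and eczema among interfering facial conditions, and eligibility is rechecked at Baseline, so such a subject should generally not be randomised.
- *That the loss is greater in the active arm.* No figure in the documents shows this.
- *That losing about three subjects matters because 1% of 300 is the cut-off for testing a term.* That cut-off is in the Fisher paragraph, which is not limited to TEAEs as worded, and it applies to each term separately, whereas the range in Step 4 is a total over all terms.

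**Conclusion.** The point holds in a limited form. As written, on-drug worsening of an AE that began in screening is left out of the summaries labelled TEAE. The severity, relationship and Fisher analyses either keep such events along with unrelated pre-dose events, or lose them, depending on a reading the text leaves open. Pre-dose events are balanced in expectation by randomisation, so they pull the comparison toward no difference without tilting it to either arm.

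The number of subjects affected is probably small and cannot be derived from the documents; 0.6 to 7.5 per arm is only what the assumed rates give. The power figures likewise rest on assumed AE rates and independence. The conclusion also assumes that sites follow the visit steps and do not open a new record on worsening, and that the separate SAP does not already resolve the matter. It is worth correcting because it concerns a stated rule and is cheap to change.

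**What to change.** 1. **Section 12.2.1, definition.** Keep the present date-based rule and add a second limb: an AE with earlier onset that increases in severity, or becomes serious, on or after that same date. Do not change the rule to strictly after the first application. Onset is collected as a date and the first application is at the Day 0 visit, so Day 0 reactions could then not be classified reliably, and a date-based reading would drop them.
2. **Section 11.4.2, recording.** For AEs ongoing at first application, have sites record the date of worsening, either as a new record or as a dated change in severity.
3. **Section 12.2.1 and Synopsis, scope.** State that the severity, relationship and Fisher's exact analyses use TEAEs so defined, and list pre-treatment AEs separately.

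The cost is a few sentences and one eCRF completion guideline. The reported TEAE rate may rise slightly. Treatment, visits and efficacy analyses are unchanged.

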## 6 Study Objectives and Purpose

The primary objective of this study is to evaluate the safety, efficacy and tolerability of a once-daily topical application of IDP-120 Gel compared to IDP-120 Vehicle Gel in subjects with moderate to severe acne vulgaris (a score of 3 or 4 [moderate to severe] on the Evaluator's Global Severity Score (EGSS) scale).

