## 9 Treatment Plan

### 9.1 Methods of Assigning Subjects to Treatment Groups

This is a double-blinded study, in which the identity of the study drug will be unknown to investigator/evaluator and subjects, as well as all individuals closely associated with the study.

Subjects will be randomized to 1 of the 2 treatment groups in a ratio of 1:1 (IDP-120 [tretinoin 0.05% and benzoyl peroxide 2.5%] Gel: IDP-120 Vehicle Gel). Each screened subject will be assigned a unique 6-digit study subject number assigned by the investigational center, which will consist of the 3-digit investigational center/site number (pre-assigned by sponsor/designee) and the 3-digit chronological screening order number, starting with 001 (e.g., 101001, 101002). The study drug kits will be assigned to subjects based on a randomization code, and a kit will be dispensed to the subjects by the IWRS at Baseline, Week 4 and Week 8 visits. A study drug log will document the inventory and dispensing of study drug at each investigational center.

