## 12 Statistics

All statistical processing will be performed using SAS® version 9.3 or later unless otherwise stated. Statistical significance will be based on two-tailed tests of the null hypothesis resulting in p-values of 0.05 or less.

The primary method of handling missing efficacy data will be based on estimation using the method of Markov Chain Monte Carlo (MCMC) imputation. This method provides robust estimation when the pattern of missingness is arbitrary. Additionally, the estimation will be done

for each treatment group separately so that the pattern of missingness for one group does not influence the estimation of missing data for another group. Groups of complete datasets following the estimation will be concatenated to form analysis datasets for the comparative analyses and subsequent imputation result inference with SAS PROC MIANALYZE. Descriptive statistics will also be derived from the multiply imputed datasets.

Additionally, a model-based multiple imputation process will be used as a sensitivity analysis to the MCMC imputation. The absolute change in lesion count will also be analyzed using a repeated measures ANCOVA for lesion count data or a repeated measures logistic regression model (generalized estimating equations) for the dichotomized EGSS. Finally, a tipping point analysis will be performed for the primary endpoints.

A statistical analysis plan (SAP), describing all statistical analyses will be provided as a separate document. The SAP will be finalized prior to unblinding of the study treatments.

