### **12.8.2 Sample Size Determination**

These power calculations are based primarily on the observed Week 12 results of the Phase 2 study, V01-120A-201. This study was a four-arm trial including IDP-120 Gel versus its individual gel components and Vehicle Gel and is therefore a relevant study for powering the current study.

A sample size of 300 per treatment arm has greater than 99% power to detect a statistically significant difference in non-inflammatory lesions with a significance level of 0.05. The estimated absolute change from baseline in treatment means were 13.3 and 8.7 for IDP-120 Gel versus its Vehicle gel, respectively, with a standard deviation of 11.0.

A sample size of 300 per treatment arm has greater than 99% power to detect a statistically significant difference in non-inflammatory lesions with a significance level of 0.05 using the estimated absolute change from baseline in treatment means of 18.8 and 7.8 for IDP-120 Gel versus its Vehicle Gel, respectively, with a standard deviation of 16.4.

In order to achieve at least 95% power to detect a statistically significant difference in the percentage of subjects who have at least a 2 grade reduction at Week 12 from Baseline in EGSS and are Clear or Almost Clear with a significance level of 0.05, a sample size of 293 per treatment group is required. The estimated percentages with a 2 grade reduction at Week 12 from Baseline in the EGSS and Clear or Almost Clear are 26.6% and 14.3% for IDP-120 Gel versus its Vehicle Gel respectively. For simplicity, a sample size of 300 per treatment arm will be used.

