### **12.8.5 Multiplicity Issues**

The overall Type I error will be controlled by requiring the three co-primary efficacy endpoints to be statistically significant. Specifically, failure of any one of the primary efficacy endpoints will invalidate the statistical significance of the secondary efficacy endpoints. See Section 12.1.6 for further detail.

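### The only statistic planned to compare adverse events between arms is an unadjusted Fisher p-value at 0.05; a descriptive risk difference with a 95% interval would show size and precision

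*Combined protocol and SAP*

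**What the plan says.** Section 12.2.1 (Adverse Events), repeated in the Safety Evaluation part of the synopsis, tabulates subjects with events by arm. It then adds a Fisher's exact test "to compare the percentage of subjects in each treatment group who report any adverse event at a significance level of 0.05". The next sentence limits the terms to those "reported by at least one percent of the subjects in any treatment group". Section 12 sets the general rule: "Statistical significance will be based on two-tailed tests of the null hypothesis resulting in p-values of 0.05 or less".

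Type I error control is described in 12.1.6 and 12.8.5 for the efficacy endpoints only: "The overall Type I error will be controlled by requiring the three co-primary efficacy endpoints to be statistically significant". Neither section mentions adverse events, and 12.2.1 gives no risk difference, risk ratio or confidence interval.

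Safety is nevertheless part of the main aim. Section 6 opens: "The primary objective of this study is to evaluate the safety, efficacy and tolerability".

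**The concern.** A p-value judged at 0.05 gives a yes/no answer and no size. For uncommon events a non-significant result is weak evidence of anything, yet nothing in the planned output would show how large an excess remains compatible with the data. If the test is run on every qualifying term, some terms may also reach 0.05 by chance, and the plan does not say how such results should be read. At stake is how informative the adverse event comparison is in a trial whose primary objective includes safety. No efficacy conclusion is affected.

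**Working it through.** **Inputs.** There are 300 subjects per arm (12.8.2: "For simplicity, a sample size of 300 per treatment arm will be used"), allocated 1:1 (9.1), with a two-sided test at 0.05 (12 and 12.2.1). The 1% filter means at least 0.01 × 300 = 3 subjects in one arm. The document gives no expected event rates and no number of terms, so these are assumed below. The safety population (12.8.1) requires confirmed use of study drug. It is taken as 300 per arm, with 270 as a check.

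**The plan's own figure.** No power or error rate is stated for adverse events. The nearest figure is 293 per group for the EGSS endpoint (26.6% v 14.3%, 95% power). With p̄ = 0.2045 and d = 0.123:

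- n' = [1.960·√(2·0.2045·0.7955) + 1.645·√(0.266·0.734 + 0.143·0.857)]² / 0.123² = 276.5
- with continuity correction, (n'/4)·[1 + √(1 + 4/(n'·d))]² = 292.5, which rounds up to 293

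The stated figure is reproduced, so 300 per arm is a sound basis for what follows.

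**Step 1: the p-value at the entry threshold.** For 3 v 0, the two-sided p is 2 × (300·299·298)/(600·599·598) = 0.249. The other splits come from the same test:

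| Split (of 300 each) | Fisher p |
|---|---|
| 5 v 0 | 0.061 |
| 6 v 0 | 0.030 |
| 9 v 3 | 0.142 |
| 11 v 3 | 0.055 |
| 12 v 3 | 0.033 |

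**Step 2: detection.** The probability that p ≤ 0.05 is Σᵢ Σⱼ b(i; 300, p₁)·b(j; 300, p₂)·1{Fisher p(i, j) ≤ 0.05}, where b is the binomial probability.

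| Vehicle to active | Fisher | Newcombe 95% CI excludes 0 |
|---|---|---|
| 1% to 3% | 31% | 39% |
| 2% to 6% | 66% | 71% |
| 3% to 9% | 85% | 88% |
| 5% to 15% | 98% | 99% |

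At 270 per arm, Fisher detection is 27% for 1% to 3% and 81% for 3% to 9%.

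**Step 3: false signals.** Setting p₁ = p₂ in the same sum gives the true size per term. It is below 0.05 because Fisher's test is conservative for rare events. Over k independent null terms, the chance of at least one p ≤ 0.05 is 1 − (1 − size)^k.

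| Common rate | True size | k = 10 | k = 20 | k = 30 |
|---|---|---|---|---|
| 1% | 1.2% | 11% | 22% | 30% |
| 2% | 2.3% | 21% | 37% | 50% |

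Using the nominal 0.05 instead would give 40% at k = 10 and 79% at k = 30, which overstates the problem.

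**Step 4: what an interval adds.** For 9/300 v 3/300 the difference is 0.030 − 0.010 = 0.020. The Wilson limits are 0.0159 to 0.0560 (active) and 0.0034 to 0.0290 (vehicle). The Newcombe limits follow:

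- lower: 0.020 − √[(0.030 − 0.0159)² + (0.0290 − 0.010)²] = −0.004
- upper: 0.020 + √[(0.0560 − 0.030)² + (0.010 − 0.0034)²] = 0.047

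So p = 0.14 becomes +2.0 points, with a 95% CI of −0.4 to 4.7.

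**Step 5: what an interval does not add.** Read as a test, the Newcombe interval flags more null terms: 3.0% per term at a 1% rate (Fisher 1.2%) and 4.1% at 2% (Fisher 2.3%). Over 20 independent null terms at 2%, the chance of at least one flag is 1 − (1 − 0.0413)^20 = 57%, against 37% for Fisher.

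**The case against.** The strongest reply is that an interval cures neither defect. Step 5 bears this out: if readers check whether it excludes zero, most 1% to 3% increases are still missed and chance findings rise. That stands. The case for the interval is estimation, not better testing.

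Second, the Fisher test is not the whole safety assessment. Section 12.2.1 also summarizes events by class, term, severity, seriousness and relationship. Local reactions are graded 0 to 3 at baseline and each later visit (11.3.1, 11.3.2, Table 1) and summarized by arm without p-values (12.2). Laboratory values and vital signs are descriptive. Per-arm percentages will be available, so the difference itself is a subtraction. This also stands, and it limits the consequence. Only the interval is truly absent, but it is what shows the excess that cannot be ruled out.

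Third, the Fisher sentence literally concerns subjects with any adverse event, and testing by term is inferred from the sentence after it. The inference is natural, since a 1% filter on terms has no function if only the overall percentage is tested, but the text should be explicit.

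Fourth, classes and the terms nested in them are not independent, so the figures in Step 3 are indicative only.

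**Conclusion.** The point holds as a gap in estimation. The plan's only statistic for comparing adverse events between arms is a p-value at 0.05, with no estimate, interval or multiplicity statement. Near the plan's own 1% cut-off it is close to uninformative: 31% detection of a 1% to 3% rise, and p=0.25 for 3 v 0. The chance of at least one false signal is about 11% to 50% over 10 to 30 terms at rates of 1% to 2%. These results rest on 300 per arm and, for false signals, on assumed term counts, rates and independence.

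Three stronger readings are tempting, and the document supports none of them:

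- **That the plan misses a threefold increase in general.** Detection depends on the vehicle rate, which is not given, and reaches 85% from 3%.
- **That a risk difference with an interval is a better test.** It shows more; it does not err less.
- **That non-significance will be taken as no difference, or significance as harm.** The plan states no such interpretation; misreading is a risk, not a planned inference.

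This is a change worth making, but the trial's main conclusions do not depend on it.

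**What to change.** In 12.2.1 and the synopsis:

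- Report the risk difference (IDP-120 Gel minus Vehicle Gel) with a 95% CI, by a named method (Newcombe or Miettinen-Nurminen), for any treatment-emergent adverse event and for each system organ class and preferred term meeting the existing 1% rule.
- Remove the 0.05 significance rule for adverse events.
- State that the intervals, and any Fisher p-values kept, are descriptive and not adjusted for multiplicity.
- Say explicitly whether comparisons are made by term as well as overall.

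The cost is wording and one table column, with no change to data collection or conduct. The downside is that a reader who treats an interval excluding zero as a signal will flag somewhat more terms by chance than with Fisher's test, which is why the descriptive label matters.
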